5.2.2 Secondary endpoint

a- Comparison of the presence of EBV infection in the cohort of patients suffering from UC and divided into the following subgroups: a) new diagnosis; b) responders to conventional therapies; c) non-responders to conventional therapies, in order to unravel whether it is a bystander or causative of the onset/relapse of the disease and whether it is responsible for refractoriness to standard of care.

b- Evaluation of the diagnostic ability in detection of EBV infection of ISH performed on mucosal specimens with respect to qRealTime-PCR.

c- Evaluation of the diagnostic ability in detection of EBV infection between qRealTime-PCR performed on peripheral blood samples with respect to mucosal specimens.

d- Evaluation of association between mucosal/blood viral load and mucosal damage as endoscopically assessed (see paragraph 5).

e- Evaluation of association between clinical index of UC activity and EBV infection.

f- Evaluation of association between steroid therapy (absent, previous or current) and EBV infection.

g- Evaluation of association between immunosuppressive therapy (absent, previous or current) and EBV infection.

h- Evaluation of association between biological therapy (absent, previous or current) and EBV infection.

i- Evaluation of the prognostic role of EBV infection on the 6 and 12 months outcome (colectomy / number of hospitalization / cause of hospitalization).

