8 STATISTICAL CONSIDERATIONS

8.1 Sample size

Sample size has been calculated based on the primary endpoint, i.e., the prevalence of EBV infection in UC patients. In UC patients non-responders to standard of care the prevalence of EBV is expected around 50%; in UC patients responders to conventional treatment may be around 10%. We hypothesize that the prevalence of EBV infection in the control population is around 0-1%. Based on the feasibility on enrolment given study design, we plan to enroll about 100 UC patients. ~~The precision achieved with 100 patients is replicated. However, the power achieved when comparing 100 patients and 100 controls is not replicated; according to our computations is much larger than that reported by the Authors (76.9% rather than 27% with a prevalence of 10% and 99.8% rather than 87% with a prevalence of 20%).~~

Prevalence	95%CI	precision	power to detect difference from control
50%	40% - 60%	10%	100%
30%	21% - 40%	9%	100%
20%	13% - 29%	8%	99,8%
10%	5% - 18%	6%	76,9%

The power to detect a significant difference with the Fisher exact test from an expected proportion in controls of 1% is above 80% for proportions of infection of 10% or greater, considering 100 patients in each group and an alpha level of 5%. Calculations are performed using Stata 17 (StataCorp, College Station, TX, USA).

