8.2 Analysis

Data will be described with the mean and standard deviation or the median and 25th-75th percentiles if continuous and as counts and percent if categorical. For the primary endpoint we will compute the prevalence as the ratio of the number of patients diagnosed with EBV infection to the number of patients evaluated, together with its 95%CI. We will use the Fisher exact test to compare the prevalence in UC patients to that of control. We will report the mean difference in proportions and its 95%CI. We will use binomial regression models with identity link (command binreg in Stata), to adjust for potential confounders, such as, but not limited to, age, gender, duration of disease and treatment. We will apply the 1:10 rule to adapt the number of confounders evaluated to the sample size. We will compare the prevalence of EBV infection between UC subgroups with the Fisher exact test (EP2a). In these cases, given in particular that the ratio of responders to non-responders is at yet unknown, we will compute *a posteriori* the power for the comparison. We will compute

sensitivity, specificity, area under the ROC curve and predictive values with 95% CIs for EP2b and EP2c. We will use the Spearman R and the Fisher exact test to assess the association, for continuous and categorical independent variables, respectively, with the dependent variables of EP2d to EP2h. All estimates will be presented with their 95% CI.

We will use Cox regression to assess the association of EBV infection with colectomy and of hospitalization for any cause; we will use Poisson regression to assess the association of EBV infection with the number of hospitalization from any cause. For secondary endpoints assessing associations, we will also fit regression models to adjust for possible confounders (as for the EP1) and report adjusted mean differences in proportions and 95% CI. We may also use propensity score inverse probability weights to account for the bias by indication when assessing treatment effect on the outcome.

The exploratory endpoints will be only descriptive.

We will use Stata 17 or later versions for computations. A 2-sided p-value <0.05 will be considered statistically significant. We will apply the Bonferroni correction for post-hoc comparisons.

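### Power computed after the data will not help to read a non-significant EP2a result; it can be tabulated now, and a null result should be read from the planned confidence interval

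*Protocol*

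**What the plan says.** Protocol 5.2.2(a) compares EBV infection in three UC subgroups (new diagnosis, responders and non-responders to conventional therapies) "in order to unravel whether it is a bystander or causative of the onset/relapse of the disease", and to see whether it accounts for refractoriness. One of the answers sought is therefore a no-difference answer.

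Section 8.2 assigns the Fisher exact test to EP2a. It then notes that "the ratio of responders to non-responders is at yet unknown" and concludes that "we will compute *a posteriori* the power for the comparison". The general criterion in the same section is "A 2-sided p-value <0.05 will be considered statistically significant", with a Bonferroni correction for post-hoc comparisons. Section 8.2 also promises 95% confidence intervals for all estimates, and adjusted differences in proportions with intervals for the secondary association endpoints.

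Section 8.1 expects a prevalence of about 50% in non-responders and about 10% in responders, among about 100 UC patients. It tabulates power for UC patients against controls only. No power is given for EP2a, and no prevalence for newly diagnosed patients.

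**The concern.** Power computed after the data is the only aid that 8.2 offers specifically for judging whether EP2a was large enough. It can mean two things, and the protocol does not choose between them.

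- **Power at the observed prevalences.** This is in effect a function of the p-value. It is low for every non-significant result, whether the subgroups are truly alike or a real difference was missed.
- **Power at the assumed 50% versus 10%, with the realised group sizes.** This is not circular. It answers only whether a 40-point difference could have been seen. A high figure can make a null result look conclusive when a smaller difference has not been excluded.

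What is at stake is how a null EP2a result is read. The question put to it is bystander or cause, and neither version of the power says how large a difference remains compatible with the data. The reason given for waiting is also weak. An unknown ratio calls for power over a range of ratios, much as 8.1 already shows power over a range of prevalences.

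**Working it through.** **Inputs.** Prevalences of 50% (non-responders) and 10% (responders), and about 100 UC patients, come from 8.1. The Fisher exact test and two-sided 0.05 come from 8.2. The subgroup splits are assumptions, since the protocol gives none. The smaller difference, 30% versus 10%, is also an assumption: both values appear in the 8.1 table, but there each is a UC prevalence set against controls.

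**Method.** Exact power = sum over all tables (a, b) with Fisher p ≤ 0.05 of Bin(a; n1, p1) × Bin(b; n2, p2).

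**Step 1: the protocol's own figures.** With 100 versus 100 and 1% in controls, UC prevalences of 50, 30, 20 and 10% give 100%, 100%, 99.84% and 76.86%. The 8.1 table has 100%, 100%, 99.8% and 76.9%, so the method matches.

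**Step 2: power at the observed prevalences.** In the normal approximation, observed power = Φ(z − 1.96) + Φ(−z − 1.96), where z is the normal deviate of the two-sided p-value:

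| p-value | observed power |
|---|---|
| 0.05 | 50% |
| 0.10 | 38% |
| 0.20 | 25% |
| 0.50 | 10% |
| 1.00 | 5% |

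Exact enumeration at 33/33 agrees: among non-significant tables the maximum is 49.7%. The mean is 24% when the truth is 30% versus 10%, and 6% when it is 10% in both groups. At 10/90, 20/80, 30/70 and 50/50 the maximum is also about 50 to 53%.

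Two results show what is lost (Newcombe intervals):

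| Result | p | observed power | 95% CI of difference, points |
|---|---|---|---|
| 5/50 vs 5/50 | 1.0 | 2% | −13 to +13 |
| 1/10 vs 9/90 | 1.0 | 2% | −11 to +31 |

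The interval separates the two cases; observed power does not.

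**Step 3: power fixed in advance.** Exact Fisher power, two-sided 0.05:

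| Non-responders / responders | 50% vs 10% | 30% vs 10% |
|---|---|---|
| 33 / 33 | 93.6% | 42% |
| 20 / 60 | 94.2% | 50% |
| 10 / 70 | 79.1% | 34% |
| 50 / 50 | 99.4% | 64% |

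For 30% versus 10%, the chance of missing the difference is 100 − 64 = 36% at 50/50 and 100 − 34 = 66% at 10/70. At 33/33, power at the assumed prevalences would be reported as 94%, while a true 20-point difference is missed in 100 − 42 = 58% of studies. If Bonferroni were applied to three pairwise comparisons (0.05/3, an assumption), the 33/33 figures fall to 86% and 25%.

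**The case against.** A reader might infer that the protocol will declare EBV a bystander on the strength of a non-significant Fisher test backed by low or high power. It states no such rule. Section 5.2.2 gives an aim, and 8.2 names a test and a power calculation. Section 8.2 also promises 95% intervals and adjusted differences, so a careful reader would have the quantity that does distinguish absence from imprecision. That stands. What 8.2 does not do is tie the interval to the reading of a null result.

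The circularity is also conditional. The input said to be missing is the group ratio, not the effect, so power at 50% versus 10% with the realised sizes is a natural reading, and it is informative about that difference. This too stands, but the text does not say so, and that version says nothing about smaller differences.

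A further tempting inference is that any difference below 40 points would usually be missed. That is not so: exact power for 40% versus 10% is 75% (33/33), 79% (20/60), 58% (10/70) and 93% (50/50). Even 30% versus 10% is detected more often than not at 50/50.

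Finally, EP2a is secondary and did not drive the sample size, and an interpretive margin may well sit in a SAP that is not shown. For that reason no margin is asked for here. The a posteriori power sentence, however, is something the protocol itself commits to.

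**Conclusion.** The point holds as one of method and wording. The planned power figure is undefined, and neither reading of it tells the reader whether a null EP2a result reflects similar prevalences or too few patients. At the observed prevalences it is capped at about 50% for non-significant results. At 50% versus 10% it is 79 to 99% over the splits tabulated above, while power for 30% versus 10% at the same splits is 34 to 64%. The unknown ratio does not prevent giving these figures beforehand.

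The sizes rest on assumed splits, on 30% versus 10% as an illustrative smaller difference, and on an unadjusted two-sided 0.05. Subgroups smaller than those shown would have less power. The primary comparison is not affected. The documents do not show that a bystander conclusion has been tied to p ≥ 0.05, and this point does not claim it.

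**What to change.** 1. In 8.2, delete the sentence on a posteriori power.
2. In 8.1, add a short table of exact Fisher power for non-responders versus responders over plausible splits (for example 33/33, 20/60, 10/70 and 50/50), at 50% versus 10% and at one smaller difference.
3. In 8.2, state that a non-significant EP2a result is interpreted from the 95% confidence interval of the prevalence difference. It is reported as inconclusive, not as evidence that EBV is a bystander, when that interval still includes differences the investigators consider relevant.

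Any numerical margin is for the sponsor to set; the protocol offers no basis for a particular value.

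The change is wording only, with no extra patients, samples or analyses, because the intervals are already planned. The cost is interpretive: null results will more often be called inconclusive, especially if one subgroup is small. The 1/10 versus 9/90 example, with identical observed prevalences and an upper limit of 31 points, shows how wide the interval can then be.

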The **control group consists of 100 sex- and age-matched subjects**, selected in the same Center, undergoing colonoscopy with mucosal sampling as diagnostic workup for IBS in order to exclude macroscopic or microscopic disorders, or because alarm features are present: aged > 45-50 years, anemia, family history of colon cancer. That are confirmed to be suffering from IBS (C1), functional constipation/diarrhea (C2, C3) and functional abdominal bloating/distension (C4), following the Rome IV criteria (48), and who were not taking drugs possibly affecting immune response (steroids, immunosuppressant and biological agents) and microbiota composition (antibiotics, probiotics, prebiotics, proton pump inhibitors).

In addition, a small cohort of patients (n=20) suffering from **microscopic colitis** will be also enrolled as pathological control group (49).

All enrolled patients and controls undergo lower endoscopy with mucosal sampling and laboratory tests as diagnostic workup for their condition:

- Patients with active UC undergo colonoscopy and laboratory tests according to International guidelines and depending on physician judgement: active UC patients will undergo colonoscopy at baseline and laboratory tests at baseline, and at 3 and 6 months. A number of these patients, according to medical judgment, undergo medical examination at 9 and 12 months, and laboratory tests and colonoscopy at 12 months as optional follow-up. This is why the aim of the study is calculated at 6 months, but adding the optional follow-up at 9 and 12 months, will aid to understand if patients with superimposed EBV colitis undergo colectomy more frequently than patients without EBV colitis
- Patients with UC in remission undergo colonoscopy and laboratory tests as standard follow-up of their pathological condition according ECCO-ESGAR guidelines [52] (ex: to evaluate mucosal healing or screening)
- Patients with IBS undergo colonoscopy and laboratory tests only if alarm features are present (age > 45-50 years, anemia, family history of colon cancer, weight loss, blood mixed with stool).

Each enrolled case will undergo clinical and/or laboratory examination as standard follow-up of his/her pathological condition. All the laboratory tests are shown in the Appendix 5.

Each patient and control give written informed consent after approval by the local Bio-Ethics Committee is obtained.

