l) The Informed Consent Form will include a statement by which the patient allows the Sponsor's duly authorised personnel, the IEC, and the regulatory authorities to have direct access to source data which supports the data on the eCRF (e.g., patient's medical file, appointment books, original laboratory records, etc.). These personnel, bound by professional secrecy, will not disclose any personal identity or personal medical information.

m) Data collection and study report form monitoring. All data obtained for this study will be entered into a regulation compliant Data Management System. Data will be recorded with an Electronic Data Capture system using eCRFs. Specifically, the Electronic Data Capture system will be based on the IGIBDReg platform. IGIBDReg is a novel workflow methodology and software tool that expedites the electronic collection of research data from a single site or multi-site clinical research study. The study database will be resident on OVH server (<https://www.ovhcloud.com/>) as required by European Certification

n) Procedure to account for missing or spurious data. In case of missing clinical assessment at follow-up visit, the last observation carried forward from the latest earlier visit will apply, while in case of missing clinical, endoscopic and histologic data by month 12, the evaluation of outcome will not be possible. We expect to have 10% patients on drop-out. IGIBDReg provides section to recording missing or N/A information.

o) Procedure to account for protocol deviations. Generally, a protocol deviation is not imperative for patient withdrawal. Before the statistical analysis begins, the protocol deviations must be taken into account for the analysis. The mandatory withdrawal reasons will be considered as major protocol deviations. Other protocol deviation will be classified as minor protocol deviation. Additionally, the lack of compliance with any of the inclusion/exclusion criterion, either identified before or after enrolment into the study, will be considered as major protocol deviation. Any protocol deviation must be recorded in the eCRF (specific section in IGIBDReg). Once the study has begun, any modification of the protocol deviation will be specified in the statistical analysis plan. This will be done before closing the database.

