14 PUBLICATION POLICY

After completion of the study, the Study Coordinator will prepare a draft manuscript containing final results of the study on the basis of the statistical analysis. The manuscript will be derived to the co-authors for comments and after revision will be sent to the appropriately selected peer-reviewed scientific journal. All information concerning this study has to be treated confidentially. In all publication/s the confidentiality of patients’ data will be ensured.

All publications, abstracts, presentations, manuscripts and slides including data from the present study will be submitted to and reviewed by the Study Coordinator for coordination and homogeneity purposes. By signing this study protocol, the investigators accept that the results of this study can be presented to national and international authorities. They also accept that in this context their name, address, qualification and grade of involvement in the trial will be published.

The Study Coordinator will be the Senior Author and the Corresponding Author of the relevant publication/s. The Authors’ list will include all the investigators (up to the maximum required by the Journal to whom the article will be submitted) in a decreasing order of patients included into the final analysis for the primary outcome, as well as the study statistician.

The funding body will be acknowledged within the publication/s, but they do not have any review and publication right on the data from the study, including their timelines for doing so.

It is responsibility of the Study Coordinator to notify the Principal Investigators of the outcome of the study by provision of the publication/s.

15 Study time table (Gantt chart)

The whole study duration is 36 months, while the time frame from the enrolment of the first patient is 32 months. The patients’ participation consists of a 3 weeks screening period, one week to undergo endoscopy with mucosal sampling and peripheral blood harvest, a 6 months mandatory follow-up period, a 6 further months of facultative follow-up period, and a 4 weeks end of study visit. Thus, the recruitment period lasts 29 months and the minimum expected duration of subject participation is of 7 months. The whole study duration is 36 months, and the subdivision of the activities by trimesters and by involved units is represented here below:

Task	I	II	III	IV	V	VI	VII	VIII	IX	X	XI	XII
1a												
1b												

Protocol code: REBUC
Effective date: 03/10/2022

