Annex 2: eCRF

Annex 3: Budget REBUC

Annex 4: Lista Centri REBUC

Appendix 1

SCCAI: Simple Clinical Colitis Activity Index

Variabile	Punteggio				
	0	1	2	3	4
Numero di scariche diurne	1 - 3	4 - 6	7 - 9	>9	
Numero di scariche notturne		1 - 3	4 - 6		
Urgenza di defecare		di corsa	immediatamente	incontinenza	
Presenza di sangue nelle feci	assente	tracce	occasionale	sempre	
Valutazione clinica globale	molto bene	lievemente al di sotto della normalità	scadente	pessima	terribile
Manifestazioni extraintestinali (1 punto per ciascuna manifestazione)					
Score totale					

Appendix 2

UCEIS: Ulcerative Colitis Endoscopic Index of Severity

Variabile	Punteggio				
	1	2	3	4	5
Pattern vascolare	normale		perdita a chiazze		obliterato
Eritema mucosale	assente		lievemente arrossata		molto arrossata
Superficie mucosale	normale		granulare		nodulare
Edema mucosale	assente		probabile		definito
Presenza di muco-pus	assente		poco		tanto
Presenza di sangue	assente	mucosale	luminale lieve	luminale moderato	luminale severo
Fragilità mucosale	assente	lieve	moderata	severa	molto severa
Fragilità mucosale al contatto	assente		probabile		definita
Presenza di erosioni-ulcere	assenti	presenza di erosioni	presenza di ulcere superficiali	presenza di ulcere profonde	
Estensione di erosioni-ulcere	assente	limitata	sostanziale	estesa	
Score totale					

Appendix 3

Schedule assessments in active UC

	Screening	Baseline	Mandatory follow-up		Optional follow-up	
			3 months	6 months	9 months	12 months
Clinical assessment	X		X	X	X	X
Body Mass Index		X	X	X	X	X
Diagnosis confirmation	X					
Clinical index of activity		X	X	X	X	X
Laboratory analyses		X	X	X		X
Blood sampling		X	X	X		X
Lower endoscopy		X				X
Endoscopic index of activity		X				X
Mucosal sampling		X				X
Histology examination		X				X
Immohistochemistry		X				X
ISH		X				X
Viral load assessment		X				X

Appendix 4

Schedule assessments in UC in remission and IBS

	Screening	Baseline
Clinical assessment	X	
Body Mass Index		X
Diagnosis confirmation	X	
Clinical index of activity		X
Laboratory analyses		X
Blood sampling		X
Lower endoscopy		X
Endoscopic index of activity		X
Mucosal sampling		X
Histology examination		X
Immunohistochemistry		X
ISH		X
Viral load assessment		X

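### Cox regression for colectomy has no provision for sparse events; if all colectomies fall in one EBV group, the standard hazard ratio is 0 or infinite

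*Protocol*

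**What the plan says.** Protocol Section 5.2.2 lists as secondary endpoint i: "Evaluation of the prognostic role of EBV infection on the 6 and 12 months outcome", with colectomy named first among the outcomes. Section 8.2 gives the method: "We will use Cox regression to assess the association of EBV infection with colectomy and of hospitalization for any cause". The same section promises a 95% CI with every estimate and limits the number of confounders by a 1:10 rule tied to sample size. It does not say what happens if colectomies are very few or all in one group.

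Section 6 explains that the optional visits at 9 and 12 months were added because they "will aid to understand if patients with superimposed EBV colitis undergo colectomy more frequently than patients without EBV colitis".

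These statements bear on the number of events:
- Section 8.1: "we plan to enroll about 100 UC patients", a number set by feasibility and judged against the prevalence endpoint.
- Section 15: "a 6 months mandatory follow-up period, a 6 further months of facultative follow-up period".
- Section 10: "We expect to have 10% patients on drop-out".
- Appendix 4, headed "Schedule assessments in UC in remission and IBS", schedules screening and baseline only.

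No colectomy rate, expected number of colectomies or hazard ratio is stated anywhere.

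**The concern.** A standard Cox model estimates the hazard ratio by maximising the partial likelihood. If all colectomies are in EBV-positive patients, the likelihood keeps rising as the hazard ratio grows. If all are in EBV-negative patients, it keeps rising as the hazard ratio falls to 0. Either way there is no finite maximum, and the standard error behind the usual Wald interval and test loses its meaning. The Wald test then tends to show no association in exactly the data sets where the split is most extreme.

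This happens with EBV status as the only covariate, so limiting the confounders does not prevent it. At stake is the finite estimate and two-sided interval promised for the outcome that motivated the optional follow-up. A rescue method chosen after the split is known would also be open to the charge of being data-driven.

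**Working it through.** **No stated figure to reproduce.** The power table in Section 8.1 concerns prevalence against controls. Its Fisher powers recompute to 76.9%, 99.8%, 100% and 100%, matching the table, but they say nothing about colectomy.

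**Inputs from the protocol.** About 100 UC patients and 10% drop-out leave 100 × 0.90 = 90. EBV prevalence in Section 8.1 is about 10% in responders and about 50% in non-responders, so the EBV-positive share q is taken from 10% to 50%.

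**Assumptions.** True HR 1 or 3; number of colectomies D = 3, 5 or 10; overall colectomy risk 2% to 20%; 90 patients followed, or 50 if a large share is in remission.

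**Chance that all events fall in one group.** With proportional hazards and small risks, each event is in an EBV-positive patient with probability

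s = q·HR / (q·HR + 1 − q),

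and P(all in one group) = s^D + (1 − s)^D.

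Example: q = 0.3, HR 1, D = 3 gives 0.3³ + 0.7³ = 0.027 + 0.343 = 0.37.

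| q | HR | s | D = 3 | D = 5 | D = 10 |
|---|---|---|---|---|---|
| 10% | 1 | 0.10 | 73% | 59% | 35% |
| 10% | 3 | 0.25 | 44% | 24% | 6% |
| 30% | 1 | 0.30 | 37% | 17% | 3% |
| 30% | 3 | 0.5625 | 26% | 7% | 0.3% |
| 50% | 1 | 0.50 | 25% | 6% | 0.2% |
| 50% | 3 | 0.75 | 44% | 24% | 6% |

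With a single event the result is certain: s + (1 − s) = 1.

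**By assumed overall risk.** These are binomial calculations, given at least one colectomy, over q = 10% to 50% and HR 1 or 3.

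| Followed | Risk | Expected events | Chance of HR 0 or infinite |
|---|---|---|---|
| 90 | 2% | 1.8 | 57–84% |
| 90 | 5% | 4.5 | 18–63% |
| 90 | 10% | 9 | 2–39% |
| 90 | 20% | 18 | 0–13% |
| 50 | 5% | 2.5 | 43–78% |
| 50 | 10% | 5 | 13–59% |

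The chance of no colectomy at all is 16% (90 followed) or 36% (50 followed) at 2% risk, and 1% or 8% at 5% risk.

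**What survives.** Take 90 patients, 27 of them EBV-positive (q = 0.3), and 4 colectomies, all in EBV-positive patients. Ignoring the small depletion of the risk set:
- The ordinary likelihood-ratio statistic is 2 × 4 × ln(1/0.3) = 9.63, above 3.84.
- The one-sided profile bound solves s⁴ = exp(−3.84/2) = 0.147, so s = 0.619 and the lower bound for the HR is (0.619/0.381) × (0.7/0.3) ≈ 3.8.

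**What Firth's penalty gives.** In the same approximation it maximises s^(D+0.5)·(1 − s)^0.5, so s = 4.5/5 = 0.9 and HR = (0.9/0.1) × (0.7/0.3) = 21. The full calculation gives HR 22 (95% CI 2.4 to 2907). With 3 colectomies, all EBV-negative, s = 0.5/4 = 0.125 and HR = (0.125/0.875) × (0.7/0.3) = 0.33; the full calculation gives 0.32 (0.0025 to 3.3).

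**Width.** In simulation (90 followed, 30% EBV-positive, HR 1 or 3), the median ratio of upper to lower limit under Firth is about 81 at 5% risk and 23 to 26 at 10% risk. Standard Cox, when finite, gives about 92 and 27. By Schoenfeld's formula, power to detect HR 3 with 5 events is 20% (30% EBV-positive) to 23% (50%).

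**The case against.** The strongest case against is that this is detail for a statistical analysis plan. Section 10 refers to such a plan, which is not shown and may contain a fallback. Section 8.2 does not name a Wald interval, and a penalised Cox model is still Cox regression. This stands as far as it goes: the point is not that detail is missing, but that the named method in its usual form can fail on plausible data and a better one is cheap to name.

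Three stronger readings are tempting, and the documents do not support them.
- A reader might infer that only a handful of colectomies can occur. The protocol gives no rate. Restricting scheduled visits to active disease reduces the number followed but may concentrate higher-risk patients. Section 6 also says every enrolled case has standard follow-up, so outcomes in remission patients are not necessarily lost.
- A reader might infer that the analysis would return nothing. The likelihood-ratio test and a one-sided bound survive, as shown above.
- A reader might infer that Firth's method rescues the endpoint. It makes the estimate finite but adds no information, and with no colectomies neither model gives an estimate.

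It is also fair that the highest probabilities need a 10% EBV-positive share, which Section 8.1 expects of responders. A followed group of active patients is unlikely to consist only of responders.

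**Conclusion.** The point holds as a low-cost improvement to one secondary endpoint; the primary analysis is untouched. With no sparse-event provision, the standard hazard ratio is 0 or infinite with probability of about 25% to 73% at 3 colectomies, 6% to 59% at 5, and under 1% to 35% at 10. These ranges rest on assumed event counts, an EBV-positive share of 10% to 50% and a true HR of 1 or 3. The problem matters mainly if about 5 or fewer colectomies occur or few patients are EBV-positive. With 90 followed and an overall risk of 10% or more it is uncommon unless the EBV-positive share is small. The conclusion concerns colectomy only; the documents give no basis for setting an event threshold for the hospitalisation analysis.

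**What to change.** In Section 8.2, or in the statistical analysis plan before the database is closed, specify for colectomy:
- Cox regression with Firth's penalised likelihood, a profile-likelihood 95% CI and a penalised likelihood-ratio test.
- Crude numbers of colectomies and cumulative incidence by EBV status, reported alongside the model.
- A descriptive report only if no colectomy occurs.
- A statement that intervals will be very wide with few events and that the penalised estimate is slightly shrunk toward no effect.

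Leave the hospitalisation analysis as it stands.

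The cost is wording; no visits, samples or patients are added. The method may need a user-written routine or other software, so the sentence restricting computations to Stata 17 or later should allow for that.
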